| | Any patient for whom a failed implant attempt is performed will be followed for 1 month, or until resolution of any potential device or implanted related adverse events, whichever occurs last. Any patient who is consented but has no implant attempt will be study exited. |

| Cerus Endovascular | Document Number DNX099-01 | Rev F | Page 8 of 106 |
|----------------------------|---|----------|---------------|
| Investigational Protocol | Title | | |
| Confidential & Proprietary | Contour Neurovascular System [™] European Pre-Market Unruptured Aneurysm Study (CERUS) | | |

| Cerus Endovascular | Document Number DNX099-01 | Rev F | Page 9 of 106 |
|----------------------------|---|----------|---------------|
| Investigational Protocol | Title | | |
| Confidential & Proprietary | Contour Neurovascular System [™] European Pre-Market Unruptured Aneurysm Study (CERUS) | | |

The Contour Neurovascular System[™] is offered in four sizes, suitable for embolization of intracranial aneurysm. Table 1 details the selection guideline for these four sizes:

The Contour Neurovascular System should only be used by operators who have received appropriate training in neurointerventional techniques. The operator delivers the implant to the aneurysm under fluoroscopic guidance using standard endovascular techniques and a commercially available 0.027" inner diameter MC¹. The implant is electrolytically detached from the DPW using a commercially available detachable coil power supply^{2,3}.

Due to its unique placement across the neck of the aneurysm, the device acts as both a flow disrupter and diverter. The Contour only requires the neck and equatorial diameter to be taken into consideration when sizing the implant to the aneurysm (please see figure below). The height is not a requirement as the dome of the aneurysm is not required to stabilize the device. The device mesh provides a uniform scaffold distributed across the neck of the aneurysm for the establishment of neointimal development and unlike devices placed in the parent vessel, is not dependent on the use of dual antiplatelet therapy.

| REF (Catalog Number) – Diameter | Aneurysm Neck (mm) | Aneurysm Width (mm) |
|------------------------------------|-----------------------|------------------------|
| CNS05 – 5 mm | 2.0 - 3.0 | 2.0 - 3.5 |
| CNS07 – 7 mm | 3.0 - 5.0 | 3.0 - 5.5 |
| CNS09 – 9 mm | 4.0 - 6.0 | 5.0 - 7.5 |
| CNS11-11 mm | 5.0 - 8.0 | 7.0 - 8.5 |

Table 1 - Implant Size Selection Guide

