| Secondary Measures | Additional measures will be summarized: | | | |
|-----------------------|---|--|--|--|
| | Secondary Safety: | | | |
| | Serious Adverse Events (SAE) associated with the procedure or device All serious neurological adverse events Secondary Performance: | | | |
| | • Detailed assessment of aneurysm occlusion from post procedure to 6-months provided by the core lab review of the angiogram (DSA) including the following: | | | |
| | - Raymond Roy scale | | | |
| | - Modified Web Occlusion Scale | | | |
| | - Percent Occlusion | | | |
| | - Device Stability | | | |
| | Rate of retreatment | | | |
| | Summary of device performance including the following: | | | |
| | - Time required for implantation of the Contour | | | |
| | - Device sizes used | | | |
| | - Number of attempts to deploy the device | | | |
| | - Number of failed implant attempts | | | |
| | - Any reports of device deficiencies | | | |
| Sample Size | A maximum of 35 subjects will be enrolled to obtain follow-up data for the primary analysis for 30 subjects while allowing for attrition to be submitted for CE Mark application. | | | |

| Number of Sites | A maximum of 10 European investigational sites will participate. |
|--------------------|---|
| Study Visits | Baseline, procedure, discharge, one (1) month, six (6) months and twelve (12) months. |

| Cerus Endovascular | Document Number DNX099-01 | Rev F | Page 13 of 106 | |
|----------------------------|---|----------|----------------|--|
| Investigational Protocol | Title | | | |
| Confidential & Proprietary | Contour Neurovascular System [™] European Pre-Market Unruptured Aneurysm Study (CERUS) | | | |

Г

| Enrollment and Eligibility | Enrollment To participate, patients must meet all inclusion criteria and no exclusion criteria listed below.All patients must sign a study-specific consent form prior to the study procedure. Final qualification will occur during the study procedure due to the need for confirmation of IA appropriateness with cerebral angiography. The patient is enrolled at the time of consent and is considered a study subject in the reporting analysis group only when the patient is fully qualified and at least one Contour device has been placed into the patient's body. The following listing provides examples of patient enrollment scenarios for the study: |
|----------------------------------|--|

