- 15. Any other medical issue within the brain that precludes the device implantation such as brain surgery, radiation in the target area of intervention, acute traumatic craniocerebral injury, etc.
- 16. Other medical conditions that cause an inability to comply with study requirements and/or that could increase the risk of neurovascular procedures or death within 2 years (e.g., liver failure, cancer, heart failure, chronic obstructive pulmonary disease, immunosuppression, neural disease, and hematologic disorders etc.)
- 17. Participating in another study with investigational devices or drugs that would confound the effects of the study outcomes

All patients must sign a study-specific consent form prior to the commencement of any protocol-specific assessments and/or procedures. Final qualification will occur during the implant procedure due to the need for confirmation of IA appropriateness with cerebral angiography.

| Cerus Endovascular | Document Number DNX099-01 | Rev F | Page 32 of 106 |
|----------------------------|--|---------------|----------------|
| Investigational Protocol | Title | | |
| Confidential & Proprietary | Contour Neurovascular System TM European Pre-M Study (CERUS) | larket Unrupt | ured Aneurysm |

The patient is enrolled at the time of consent and is considered a study subject in the reporting analysis group only when the patient is fully qualified and at least one Contour device has been placed into the patient's body. The following listing provides examples of patient enrollment scenarios for the study:

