- The patient is not considered enrolled but not included in the primary analysis group in the study: if at the onset of the procedure in the initial DSA, the investigator determined the patient's IA was not suitable for treatment with the device, thus, no attempt was made by the investigator to place the device. The patient will be treated outside of the study per the investigator's usual practices. The reason for not treating the patient must be documented on a study exit form. The patient is not included in the primary analysis group because the Contour was never opened or deployed inside the patient. All patients will be listed in the final report. The patient is considered enrolled but not included in the primary analysis group in the study: at the onset of the procedure, the investigator attempted but was unable to place the device within the IA and the subject required alternative treatment. The subject is considered enrolled for the purposes of the study but will only be followed through the 1-month visit. All failed implant attempts will be reported in the final report.
- The patient is considered enrolled and included in the primary analysis group in the study: if at the onset of the procedure, the investigator determined the subject's IA was suitable for treatment with the device. The investigator successfully placed the device within the IA. The subject is considered enrolled for the purposes of the study and will be followed for the duration of the study.
- The patient is considered enrolled and included in the primary analysis group in the study: if at the onset of the procedure, the investigator determined the subject's IA was suitable for treatment with the device. The investigator successfully placed the device within the IA. In addition, the subject required and received further treatment with another endovascular device(s). The subject is considered enrolled for the purposes of the study and will be followed for the duration of the study.

The available sizes of the Contour implant along with coordinating aneurysm dimensions and definitions are provided in Figure 3.

| REF (Catalog Number) – Diameter | Aneurysm Neck (mm) | Aneurysm Width (mm) |
|------------------------------------|-----------------------|------------------------|
| CNS05 – 5 mm | 2.0 - 3.0 | 2.0 - 3.5 |
| CNS07 – 7 mm | 3.0 - 5.0 | 3.0 - 5.5 |

| Cerus Endovascular | Document Number DNX099-01 | Rev F | Page 33 of 106 |

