8.2 Adverse Event Classification

8.2.1 AE Severity:

The severity of an AE is a qualitative judgment of the degree of intensity, as determined by the Investigator or as reported by the subject. The severity of the AE shall be evaluated according to the following scale:

| Cerus Endovascular | Document Number DNX099-01 | Rev F | Page 39 of 106 |
|----------------------------|---|---------------|----------------|
| Investigational Protocol | Title | | |
| Confidential & Proprietary | Contour Neurovascular System [™] European Pre-M Study (CERUS) | 1arket Unrupt | ured Aneurysm |

- Mild no limitation of usual activities, no therapy or only symptomatic therapy required to treat the injury or illness.
- Moderate some limitation of usual activities or specific therapy is required.
- Severe inability to carry out usual activities, hospitalization, emergency treatment, life threatening events, or death.

The assessment of severity shall be made independent of the relationship to the device and therapy or the seriousness of the event.

8.2.2 AE causality:

Each AE shall be assessed by the Investigator for its relationship to the use of the study device or study procedure as outlined below.

Device Related: Restricted to the study device.

Procedure Related: Restricted to the implant procedure and any procedure associated directly with placement of the device.

Definitely related: An AE is definitely related to a specific category if it is obvious, certain or there is little doubt regarding the relationship.

Possible related: An AE is possibly related to a specific category if it is capable of being related but relatively unlikely.

Not related: An AE is not related to a specific category if it is determined that there is no plausible association.

Subjects experiencing AEs shall be offered comprehensive medical care for conditions associated with the implant procedures and followed until their medical outcomes are resolved.

| AEs | Non- DeviceRelated | Device-Related | | Device Deficiencies* |
|-------------|-----------------------|----------------|---------------|------------------------|
| Non-Serious | AE | ADE | | Without SADE potential |
| Serious | SAE | SADE | | With SADE potential |
| | | Anticipated | Unanticipated | |

Table **6**. AE Categorization

| Cerus Endovascular | Document Number DNX099-01 | Rev F | Page 40 of 106 |
|----------------------------|---|---------------|----------------|
| Investigational Protocol | Title | | |

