10.7 Sample Size Rationale

This is a single arm study designed to provide adequate data for the purpose of CE Mark. It is expected the 30 patients with evaluable data at 6 month follow-up will show adequate evidence of safety and performance for the application for CE Mark of the device. No formal hypothesis testing of the study endpoints will be performed, therefore no formal sample size was calculated.

11 Additional Trial Characteristics

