11.5 Total Expected Trial Duration

The enrollment period is expected to take 9 months and the follow-up duration is expected to be 6 months to obtain data for the primary analysis. The study population will include 30 subjects enrolled and implanted at up to 10 centers in Europe with evaluable data at 6 months for the analysis for CE Mark. It is expected that the study will take 9 months to enroll the first 30 patients and continue up to 9 months for the initial report for CE Mark.

All patients must be consented prior to performing study related procedures. All patients that provide consent and are implanted will be followed according to the follow-up schedule. Any patient for whom a failed implant attempt is performed will be followed for 1-month or until resolution of any potential device or implanted related adverse events, whichever occurs last.

12 Study Management

This study will be managed according to ISO 14155:2011, the Declaration of Helsinki in its current revision, conditions imposed by local ethics committees (ECs), and any applicable regulatory requirements. For this study, the sponsor will have certain direct responsibilities and may delegate other responsibilities to appropriate consultants and/or contract research organizations (CROs). Together, the sponsor and all related participants will ensure that the study is conducted according to the above standards and all applicable regulations. All personnel to participate in the conduct of this clinical trial will be qualified by training, education and/or experience to perform his or her respective tasks.

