12.2.11 Study Close Out

When the investigation is complete, the sponsor will ensure that sites undergo closeout activities, to include:

- all essential documents are available and present in the PI's files
- all CRFs are completed
- all queries are resolved
- the status of all ongoing AEs is documented
- arrangements for record retention have been made
- all documents needed for sponsor's files are retrieved
- unused study devices are accounted for and returned to the sponsor
- local EC and regulatory authorities are notified, if applicable In addition, the sponsor will:
- provide a clinical investigation report to sites
- ensure that clinical investigational report is provided to EC, investigators and regulatory authorities (if required)

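### Section 7.5 ends follow-up of failed-attempt subjects at 1 month, while the synopsis, Section 11.5 and SAP Section 5 continue it until related adverse events resolve

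*Protocol*

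**What the plan says.** Four places in the current text set the length of follow-up for a failed implant attempt.

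- **Protocol 7.5**, in the scenario where the investigator tried but could not place the device and another treatment was needed: the subject counts as enrolled "but will only be followed through the 1-month visit".
- **Protocol synopsis**, Study Size and Duration: the patient is "followed for 1 month, or until resolution of any potential device or implanted related adverse events, whichever occurs last".
- **Protocol 11.5**: the patient is "followed for 1-month or until resolution of any potential device or implanted related adverse events, whichever occurs last".
- **SAP Section 5**: repeats the synopsis sentence.

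Two further statements bear on the point. Protocol 8.2.2 says subjects with adverse events receive care for "conditions associated with the implant procedures and followed until their medical outcomes are resolved". Protocol 12.2.11 requires at close-out that "the status of all ongoing AEs is documented".

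**The concern.** The word *only* in 7.5 makes 1 month a maximum. In the other three places the later of two dates applies, which makes 1 month a minimum. Investigators may not depart from the plan except in limited circumstances (Protocol 12.1.6 and 12.1.14), so a site needs one rule.

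A site that applies 7.5 literally could exit a subject whose device- or implant-related event is still open at 1 month. A site that applies 11.5 would keep the same subject under observation. Serious adverse events associated with the procedure or device are a secondary safety endpoint (Protocol 10.5.2), and the analysis takes in all available data on all enrolled subjects (Protocol 10.3). Failed attempts are enrolled, so the course and outcome of their events belong to the safety record submitted for the CE Mark.

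**Working it through.** **Comparison of the rules.** The plan gives no figure to reproduce here; the check is a reading of the texts against each other. Let T be the time at which the last potentially device- or implant-related event resolves.

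| Source | Follow-up ends at |
|---|---|
| Protocol 7.5 | 1 month |
| Protocol synopsis, Protocol 11.5, SAP 5 | max(1 month, T) |

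- No related event, or T ≤ 1 month: both rules give 1 month, so there is no conflict.
- T > 1 month: 7.5 gives 1 month and the others give T. This is the situation for which the extension was written.

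**Could another provision settle it?**

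- The introduction to the 7.5 list reads "The following listing provides examples of patient enrollment scenarios for the study". Even as an example, the sentence gives a follow-up instruction. The two implanted scenarios in the same list also set follow-up, for the full study.
- The schedule of assessments does not help. The synopsis applies scheduled follow-up to implanted subjects, so a failed-attempt subject depends on the conflicting sentences.
- Close-out under 12.2.11 asks for the status of open events to be recorded. It does not require follow-up to resolution.

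**How many subjects the rule can govern.**

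- Enrollment cap, from the synopsis Sample Size row: "A maximum of 35 subjects will be enrolled to obtain follow-up data for the primary analysis for 30 subjects while allowing for attrition".
- Expected evaluable number, from Protocol 10.7: "30 patients with evaluable data at 6 month follow-up".
- Protocol 7.5 counts a failed attempt as enrolled but outside the primary analysis group, so a failed attempt is not one of the 30.

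Maximum failed attempts if the target is met = 35 − 30 = 5, and 5/35 = 14.3% of those enrolled. Attrition after implantation, and consented patients with no attempt if they count as enrolled, draw on the same 5. The range is therefore 0 to 5. The conflict affects only those among them with T > 1 month. The documents give neither a failed-attempt rate nor a rate of events open at 1 month, so the range cannot be narrowed.

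**The case against.** The strongest reply is that subjects are already protected. Section 8.2.2 is addressed to the same kind of event and tells sites to follow it to resolution, so exiting a subject with an open implant-related event would breach 8.2.2 as well as the synopsis and 11.5. On this view, 7.5 only says which scheduled visits apply (1 month, not 6 or 12), and it is incomplete rather than wrong. This establishes which rule is intended and makes harm less likely. It does not remove the conflict: the sentence in 7.5 limits follow-up itself, without confining the limit to scheduled visits, and makes no exception for open events.

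A second objection is that the limit of 5 is insecure. The 30 evaluable subjects are an expectation, and the text is unclear on whether a consented patient with no attempt counts as enrolled. The first part stands: the limit is conditional on reaching 30. The second does not affect the limit for failed attempts, because 7.5 expressly counts those as enrolled. The 14.3% is a ceiling on the group covered by the rule and says nothing about how often the problem will occur.

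A third objection is that follow-up to resolution has no end date, so a permanent deficit could keep a subject in follow-up indefinitely. That is a fair remark about the longer rule. The plan already states that rule three times, however, so aligning 7.5 with it adds no new obligation.

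**Conclusion.** The inconsistency is real, and Section 7.5 is wrong as written. It is minor: the intended rule is plain from three other places and is supported by 8.2.2, and no primary result, sample size or planned analysis changes. It should still be corrected, because it is a safety follow-up instruction and the clause that limits follow-up appears in the section sites use to classify subjects.

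The rule governs 0 to 5 subjects, provided that no more than 35 are enrolled, failed attempts count towards the 35 as 7.5 says, and 30 subjects are evaluable at 6 months. Only those with a related event open at 1 month are affected. The contradiction itself depends on none of these numbers.

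**What to change.** In Protocol 7.5, delete the limiting clause and state that the subject will be "followed for 1 month, or until resolution of any potential device or implanted related adverse events, whichever occurs last". The synopsis, Section 11.5 and SAP Section 5 need no change.

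Check the synopsis copy of the enrollment scenarios and make the same edit there if it carries the same clause. That list is garbled in the text available for this review, so its wording could not be confirmed.

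The cost is one clause, possibly two, with the ethics committee and authority notification or approval described in Protocol 12.2.4. The added burden is longer follow-up for the few failed-attempt subjects with an open related event, at most 5 if the 30-subject target is met. The documents do not say how long that follow-up would last.

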7.6 Baseline Evaluation

The baseline evaluation is performed after signing the consent form and prior to the implant procedure. During the baseline evaluation, the investigator and/or coordinator will record basic medical information on the study case report form (CRF), including known diagnoses and daily medication use. Any relevant neurologic findings will be recorded on the CRF. A modified Rankin Scale (mRS) will be performed at baseline. The mRS is a widely used scale for measuring the degree of disability or dependence in the daily activities of people who have suffered a stroke or other causes of neurological disability.

All images obtained at screening or from images obtained prior to screening as standard, including the 3D angiogram, MRA and/or CTA are to be submitted for review to the patient selection committee to confirm the subject's eligibility for use of the Contour Neurovascular System. The Contour Neurovascular System procedure may be scheduled following confirmation from the committee. Additionally, the images obtained at baseline shall be submitted to the independent core laboratory.

7.6.1 Angiogram

A cerebral angiogram that includes a 3D rotational angiogram shall be performed prior to the Contour Neurovascular System implant placement procedure to allow proper assessment of the target IA being treated. The angiogram will include the acquisition of a 3D rotational angiogram of the aneurysm and parent vessel. Imaging will always be performed on the day of the procedure which will be used for core laboratory baseline for comparison at 6 months. All imaging must be submitted to the independent core lab for analysis.

| Cerus Endovascular | Document Number DNX099-01 | Rev F | Page 34 of 106 |
|----------------------------|--|---------------|----------------|
| Investigational Protocol | Title | | |
| Confidential & Proprietary | Contour Neurovascular System TM European Pre-M Study (CERUS) | 1arket Unrupt | ured Aneurysm |

7.7 Implant Procedure

7.7.1 Preoperative Preparation

The subject undergoes standard preoperative preparation. The device implant procedure must be performed under general anaesthesia.

7.7.2 Arterial Access

Standard methods are used to gain access to the femoral artery. Standard methods are used (e.g., sheaths and guide catheters, distal support guides) to obtain access to the IA. Tri-axial approach, although not mandatory, is highly recommended.

